### **6.11.1.1. Corticosteroids**

#### **6.11.1.1.1. Oral Corticosteroids**

Stable use of oral corticosteroids  $\leq$ 10 mg/day prednisone or equivalent agent is permitted if the dose is stable for at least 28 days prior to Day 1 (baseline). This dose should remain constant throughout the first 12 weeks of the study. Dose reductions before Week 12 are not permitted, unless required for safety or tolerability.

If the corticosteroid dose is increased above 10 mg/day prednisone, the subject will be deemed a treatment failure and investigational product will be discontinued, although the subject will remain on study and undergo study visits as outlined in the Time and Event Table Section 7.1.

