### **6.11.3. Prohibited Medications and Non-Drug Therapies**

#### **6.11.3.1. Related to the Study**

- Any conventional DMARDs other than MTX (including hydroxychloroquine, leflunomide, sulphasalazine, minocycline, ciclosporin, azathioprine).
- Any biologic agent (such as TNF inhibitors such as adalimumab, etanercept, infliximab, certolizumab pegol, golimumab or non-TNF inhibitors (including abatacept, rituximab, tocilizumab and belimumab) and any anti-rheumatic investigational compounds.
- IA corticosteroids are strongly discouraged within 8 weeks prior to Day 1, and then through Week 52.
  - However, IA corticosteroids may be used in a limited fashion as treatment for severe RA flares.
  - No more than 1 joint per 24-week period or 2 joints per 52-week period should be injected.
  - No single injection should exceed 40 mg of triamcinolone (or equivalent) and the total dose of IA corticosteroid should not exceed 80 mg of triamcinolone (or equivalent) during the 52-week period.
- IV and/or IM steroids are not permitted for at least 28 days prior to Day 1, or throughout the study.
- Live vaccines should not be administered for 12 weeks after the last dose of GSK3196165. Furthermore, GSK3196165 and MTX are immunosuppressive and may therefore reduce immunological response to concurrent vaccination. In addition, investigators are expected to assess vaccination status, including against influenza and pneumococcus according to local guidelines.

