Anti-GM-CSF auto-antibodies 		X 																																			
Study Treatment GSK3196165/placebo (Methotrexate and folic acid weekly throughout treatment with GSK3196165)		X	X	X	X	X	X	X	X	X	X	X	X	X	X	X	X	X	X	X	X	X	X	X	X	X	X	X	X	X	X	X	X				
Rescue point for possible dose escalation											X								X																		
Decision point for mandated withdrawal 																																					

1. All subjects who discontinue study medication prematurely should have an early withdrawal (EW) visit as soon as possible after study agent discontinuation and then return for a follow-up safety visit at least 12 weeks after last dose of study medication.
2. The same individual (where possible) should perform all disease assessments for an individual subject (with separate joint assessor).
3. All PRO assessments should be conducted before any tests, procedures, assessments or consultations, to avoid influencing the subjects' perception.
4. Assessments may be performed up to 24 hours before dosing GSK3196165.
5. Non-actigraphy sub-study subjects only.
6. Performed in a subset of consenting subjects only.
7. Actigraphy device placed and tagging process started (as detailed in the SRM), RA Symptom and Impact Diary questionnaire started on the same day at home using an electronic PRO (ePRO) device and completed on a daily basis until next visit.
8. Actigraphy device collected and RA Symptom and Impact Diary questionnaire completed at site visit and ePRO device collected.
9. All safety evaluations should be conducted before dosing GSK3196165.
10. Complete physical at baseline, and then limited physical examination (abdominal examination and heart sounds) thereafter.
11. ECG should be performed before vital signs, blood draws, and dosing.
12. Unless performed within previous 12 weeks (No need to repeat if subject re-screened).
13. Chest HRCT if  $D_{LCO} \geq 60\% - < 70\%$  predicted (No need to repeat if subject re-screened).
14. If the screening  $D_{LCO}$  value is  $\geq 70\%$  predicted, but the subsequent "Day 1" value is  $< 70$  but  $\geq 60\%$  predicted, the  $D_{LCO}$  test must be repeated if still within the screening window. If the repeat value is  $\geq 70\%$ , the "Day 1" activities may be completed, but if the value is again  $< 70\%$ , dosing must be postponed and a chest HRCT performed. If this cannot be done within the screening window then the subject must be re-screened.

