#### 4.3.1 Analysis Datasets

For each of the efficacy evaluations of binary endpoints, subjects with missing efficacy data, early withdrawals, subjects who received more than 10 mg/day of prednisone equivalent oral corticosteroids, subjects with any new use of parenteral corticosteroids, more than one intra-articular corticosteroid injection within a 24 week period, or subjects who received rescue treatment will be imputed as non-responders and therefore treated as a failure (e.g. no DAS28(CRP) remission or no moderate/good EULAR response). Imputation rules for each case are described in section 4.5.2:

A dataset will be created with these imputation rules and will be referred to as the NRI dataset. The NRI dataset will be the primary dataset used for all binary efficacy endpoints. Imputed response for each binary endpoint will be presented by visit and subject in listings.

For the efficacy evaluations of continuous endpoints, results recorded for subjects who received rescue treatment or exceeded 10 mg/day prednisone equivalent oral corticosteroids, subjects with any new use of parenteral corticosteroids, more than one intra-articular corticosteroid injection within a 24 week period, or subjects who received rescue treatment will be set to missing at the same visits that were set to non-responder for the binary endpoints. This is a change from protocol section 9.3.2. A dataset will be created and will be referred to as the Set-to-Missing (STM) dataset.

For safety endpoints, no imputation for missing data will be done.

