## 4.5.2 Missing Data for Efficacy and Safety Endpoints

### 4.5.2.1 Missing Data for Efficacy Endpoints

Missing visit data for each efficacy endpoint will be handled as described in Sections 3.2 and 4.3.1. For each continuous endpoint, change from baseline will be missing at visits with missing post-baseline values or where data were imputed to missing.

For the binary endpoints, subjects with missing efficacy data, early withdrawals, subjects who exceed the allowed dose of corticosteroid, who received new parenteral corticosteroids or more than one intra-articular corticosteroid injection within a 24 week period, or subjects who received rescue treatment will be imputed as non-responders and therefore treated as a failure (e.g. no DAS28(CRP) remission or no moderate/good EULAR response).

For subjects who exceed the allowed dose of corticosteroid, who received new parenteral corticosteroids or more than one intra-articular corticosteroid injection within 24 weeks or subjects who received rescue treatment, continuous efficacy endpoints will be set to missing.

- Missing efficacy data: visits with missing data (due to a missed visit or missing component of a composite endpoint) should be set to treatment failure.
- Early withdrawals (including subjects that are withdrawn at Week 36 due to lack of EULAR response): only visits following the early withdrawal visit should be set to treatment failure.
- Prednisone equivalent >10 mg/day: the visit after a period (time from previous visit up to the day before the current visit) of average daily corticosteroid use exceeding 10 mg/day prednisone and all following visits should be set to treatment failure (continuous endpoints will be set to missing).
- Parenteral corticosteroids: all visits after a subject received any new parenteral corticosteroids (e.g. intravenous and intra-muscular) should be set to treatment failure (continuous endpoints will be set to missing).
- Intra-articular corticosteroids: all visits after the second intra-articular corticosteroid injection within a 24 week period should be set to treatment failure (continuous endpoints will be set to missing).
- Rescue: subjects who rescue to 180 mg dose at Week 14 or 26 should be set to treatment failure at that visit and all subsequent visits (continuous endpoints will be set to missing).

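### The SAP averages oral steroid use between visits, so a short course that the protocol calls a treatment failure can still be scored as Week 24 remission

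*SAP*

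**What the plan says.** **Protocol, 6.11.1.1.1 Oral Corticosteroids.** "If the corticosteroid dose is increased above 10 mg/day prednisone, the subject will be deemed a treatment failure and investigational product will be discontinued". Even so, the section keeps such a subject in the trial on the regular visit schedule. The trigger is a dose increase. No averaging and no minimum duration is mentioned.

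**SAP, 4.3.1 Analysis Datasets.** The non-responder list includes "subjects who received more than 10 mg/day of prednisone equivalent oral corticosteroids", also without averaging, but the section sends the reader to 4.5.2 for the detailed rules.

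**SAP, 4.5.2.1.** The operative rule fails the visit that follows a between-visit period of "average daily corticosteroid use exceeding 10 mg/day prednisone and all following visits should be set to treatment failure". Continuous endpoints go to missing at the same visits. For early withdrawals, only visits after the early withdrawal (EW) visit are failed. The rescue bullet covers escalation to 180 mg at Week 14 or 26 and nothing else.

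**EW visits.** Footnote 1 of the Time and Events Table, in both documents, states: "All subjects who discontinue study medication prematurely should have an early withdrawal (EW) visit as soon as possible after study agent discontinuation". SAP 3.1.1 repeats the instruction. SAP 4.5.3 maps EW visits to scheduled visits.

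**SAP, 4.14.** It declares that continuous results will be set to missing after excess steroid use. It does not mention averaging.

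**Protocol, 6.11.3.1.** Prohibited treatments include "Any conventional DMARDs other than MTX" and any biologic agent.

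**The concern.** The primary endpoint is DAS28(CRP) remission at Week 24 under non-responder imputation. Its meaning depends on which events turn an observed score below 2.6 into a failure. Here the two documents use different triggers for the same event, and the SAP does not say so.

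A short course above 10 mg/day is diluted by the other days in the interval. The protocol counts that subject as a failure and stops product, yet keeps the subject attending visits, so a Week 24 score can exist. If the score is below 2.6, the SAP can count remission on the randomised dose for a subject who is off that dose. The same rule drives set-to-missing, so the continuous endpoints share the gap.

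A separate omission lies in the same list. A subject who starts a prohibited DMARD or biologic and stays on study meets none of the listed failure rules.

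**Working it through.** **1. The plan's own figure.** Inputs from Protocol 9.2.1.1 and SAP 4.13.1: 35 per arm, 33% against 3%, Fisher's exact test, two-sided 0.05. Exact enumeration over two binomial arms gives 90.9% power, against the stated value of about 90%.

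**2. What the averaged rule lets through.** Week 22 is Day 155 and Week 24 is Day 169, an interval of 14 days. With baseline dose b, raised dose r and d days at r:

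average = [b × (14 − d) + r × d] / 14, flagged only if above 10, that is, if the interval total exceeds 10 × 14 = 140 mg.

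| b (mg/day) | r (mg/day) | d (days) | average (mg/day) |
|---|---|---|---|
| 0 | 20 | 6 | 120/14 = 8.57 |
| 0 | 20 | 7 | 140/14 = 10.0 (not above 10) |
| 0 | 40 | 3 | 120/14 = 8.57 |
| 5 | 15 | 6 | (40 + 90)/14 = 9.29 |
| 5 | 20 | 4 | (50 + 80)/14 = 9.29 |
| 7.5 | 20 | 2 | (90 + 40)/14 = 9.29 |

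All six rows are failures under Protocol 6.11.1.1.1 and none is flagged by the SAP. A subject already on a stable 10 mg/day has no such slack: any increase is flagged. If a missed visit stretches the interval to 28 days, 9 days at 20 mg from 5 mg also pass: (19 × 5 + 9 × 20)/28 = 275/28 = 9.82.

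**3. Timing.** The fifth row can be a continuing increase: 5 mg/day raised to 20 mg/day on Day 165, with the Week 24 visit on Day 169. Days 155 to 164 contribute 50 mg and Days 165 to 168 contribute 80 mg. Week 24 is not failed. A continuing increase that starts before Day 155 fills the whole interval, so Week 24 is failed.

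**4. Does the EW rule close the gap?** Under SAP 4.5.3, from Week 4 an EW visit more than 7 days after a target day goes to the next visit. Day 155 + 8 = Day 163 and Day 169 + 7 = Day 176, so an EW visit on about Days 163 to 176 is assigned to Week 24 itself. Only later visits are failed.

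- EW visit held and mapped before Week 24: Week 24 is a failure and the gap is closed.
- EW visit on about Days 163 to 176: Week 24 is not failed.
- No EW visit, the subject continuing on the regular schedule as Protocol 6.11.1.1.1 describes: Week 24 is not failed.

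**5. The two averaging windows differ.** SAP 4.5.2.1 ends the window the day before the visit. SAP 4.5.4 includes the visit day but divides by the date difference. If the previous visit day is also counted, a constant and permitted 10 mg/day gives 15 × 10/14 = 10.7 and would be failed wrongly.

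**6. Size.** One subject is 1/35 = 2.9 points; 3% of 35 is about one expected placebo remitter. The documents give no frequency for these courses. As an illustration only, assume about one masked failure per 35 (3 points) counted as a remitter. Exact Fisher power is then:

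- none: 90.9%
- placebo only (33% against 6%): 77.9%
- both arms (36% against 6%): 85.3%
- active only (36% against 3%): 94.9%

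The direction depends entirely on where the cases fall.

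**The case against.** The best defence has four parts.

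- **Scope.** Failure carries forward once set, so a sustained increase begun well before Week 24 is caught. This stands. A reader might infer that any subject taken off drug for steroids can count as a remitter; the documents do not support that.
- **EW visits.** If product stops and sites hold the EW visit promptly, as both documents ask, most earlier courses become Week 24 failures whatever the average. This stands for EW visits mapped before Week 24. It does not cover EW visits mapped to Week 24, or sites that keep the subject on the regular schedule. An EW assessment does not by itself rule out later visits, so the two instructions are in tension rather than flatly contradictory.
- **Averaging as a choice.** A limit in mg/day can be read as a rate, and Protocol 9.4 leaves analysis detail to the plan. Protocol 9.3.2 lists no steroid rule at all, so the SAP is adding protection. That is fair, but the choice is undeclared and departs from the protocol's own definition of failure.
- **DMARDs and biologics.** SAP 4.3.1 fails subjects who received rescue treatment, the heading of Protocol 6.11.2 names DMARD and biologic rescue, and SAP 4.4.2 tracks disallowed medications as deviations. But the operative bullet is limited to 180 mg escalation, a deviation category does not set failure, and the withdrawal list in Protocol 5.4 does not name prohibited medication.

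**Conclusion.** The mismatch is real but narrow. Two kinds of protocol-defined failure can be scored as Week 24 remission: short courses above 10 mg/day that average 10 or less, and increases that start within days of the visit. Both require that no EW visit was mapped before Week 24 and that the observed DAS28(CRP) is below 2.6. The omission of prohibited DMARD or biologic use is a separate gap in the same list.

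A reader might infer that the rule shrinks the difference from placebo, because flares should be commoner in weaker arms, or that it inflates the 180 mg arm, which has no escape. Neither follows from the documents. Week 12 EULAR non-responders in every other arm escalate and are failed from Week 14, which changes who is left to be misclassified, and no frequency of steroid courses is given. The 2.9 points per subject is exact; the power figures rest on an assumed count.

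This should be corrected before unblinding because it concerns classification of the primary endpoint and is cheap to settle. Nothing in the documents shows that it would overturn the primary result, so it ranks below the issues that must be resolved before the analysis can stand.

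**What to change.** In SAP 4.5.2.1, set binary endpoints to failure and continuous endpoints to missing from the first visit after any of these:

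- a recorded oral dose increase above the threshold in Protocol 6.11.1.1.1;
- stopping of product for that reason, including when the EW visit is itself mapped to Week 24;
- the start of a DMARD or biologic prohibited in Protocol 6.11.3.1.

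Keep the averaged steroid rule as a sensitivity analysis. If averaging is intended, declare it in SAP 4.14 and run the dose-level rule as the sensitivity analysis.

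Reconcile Protocol 6.11.1.1.1 with the EW instruction in the Time and Events footnote and SAP 3.1.1, and align the averaging windows in SAP 4.5.2.1 and 4.5.4. Which clinical rule applies is for the sponsor to settle.

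The cost is wording and a few lines of programming, since concomitant medications are already recorded. The downside is a few more non-responders. A dose-level trigger also needs a convention for overlapping start and stop dates and for partial dates imputed under SAP 4.5.1, so that a compliant subject is not failed permanently by a date artefact.

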**Prior to AND throughout the study:**

- Any conventional DMARDs other than MTX (including hydroxychloroquine,

sulphasalazine, minocycline, ciclosporin) should be withdrawn at least 2 weeks prior to Day 1.

- Subjects may require longer to discontinue azathioprine or leflunomide prior to randomization:
  - Azathioprine must be discontinued  $\geq$ 28 days prior to randomization.
  - Leflunomide must be discontinued  $\geq$ 12 weeks prior to randomization (or  $\geq$ 14 days after 11 days of standard cholestyramine or activated charcoal washout).
- **For these subjects, written informed consent for the study (or sub-studies) must be obtained prior to beginning the screening period.** However, other screening assessments, other than consent, must occur within 28 days prior to randomization.
- Any biologic agents (such as TNF inhibitors such as adalimumab, etanercept, infliximab, certolizumab pegol, golimumab or non-TNF inhibitors (including abatacept, rituximab, tocilizumab, belimumab).
- Any anti-rheumatic investigational compounds.
- Any alkylating agents (such as cyclophosphamide or chlorambucil).
- Plasmapheresis or intravenous immunoglobulin (IVIG) within 26 weeks of Day 1.

18. Corticosteroids:

- Any IM, IV or IA corticosteroids within 8 weeks of Day 1.
- Oral corticosteroids:
  - Any treatment with  $>10$  mg/day dose oral prednisolone (or equivalent) within 28 days of Day 1.
  - New oral corticosteroid or changes in corticosteroid dose within the 28 days prior to Day 1. (New topical steroids and immunosuppressive agents (e.g., eye drops, creams) are permitted).

19. Non-steroidal anti-inflammatory drugs (NSAIDs):

- New or change in dose of NSAID within 14 days of Day 1.

20. Any non-anti-rheumatic investigational treatment must be discontinued for at least 4 weeks or 5 half-lives, whichever is longer, prior to Day 1.

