### **3.2.3 Swollen and Tender/Painful Joint Count**

Four different scores will be calculated to evaluate swelling and tenderness of joints. TJC28 and SJC28 will take 28 joints into account, SJC66 and TJC68 will use 66 and 68 joints, respectively.

The assessment for swelling is the total number of joints with a present swelling and ranges from 0 to 28 for SJC28 and 0 to 66 for SJC66.

The assessment for tenderness is the total number of joints with a present tenderness and ranges from 0 to 28 for TJC28 and 0 to 68 for TJC68.

The following 28 joints will be taken into account for TJC28 and SJC28: Shoulder (2 joints), Knee (2), Elbow (2), Wrist (2), Fingers (PIP, MCP: 20).

Additionally the following joints will be taken into account for SJC66/TJC68: Temporomandibular (2), Sternoclavicular (2), Acromioclavicular (2), Fingers (DIP: 8), Ankle (2), Tarsus (2), Toes (PIP, MTP: 20), Hip (2, only for TJC). Artificial, ankylosed and missing joints are excluded from swelling and tenderness assessment.

If there are missing observations for tender or swollen joints then the remaining observations will be assessed and weighted by dividing the number presented by number of non-missing and by

multiplying by 28/66/68 for the joint count. No imputations for individual joints will be done. If a joint is not evaluable at Baseline, then that joint is set to missing throughout the study.

If data for more than 50% of the joints are missing at the time of a given assessment, then the total count will be set to missing for that visit.

Observed joint states will be listed without any modification for every subject and visit.

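### A first intra-articular steroid injection leaves the injected joint scored as observed, and in a subject with few active joints this alone can bring DAS28(CRP) below the 2.6 remission cut-off

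*SAP*

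**What the plan says.** - **Use on study.** Protocol 6.11.3.1 discourages IA steroid through Week 52 but states that "IA corticosteroids may be used in a limited fashion as treatment for severe RA flares". The cap is "No more than 1 joint per 24-week period or 2 joints per 52-week period should be injected". Nothing ties the timing of an injection to efficacy visits.
- **Analysis consequence.** SAP 4.3.1 defines the non-responder dataset so that subjects with "more than one intra-articular corticosteroid injection within a 24 week period, or subjects who received rescue treatment will be imputed as non-responders". SAP 4.5.2.1 gives the timing: "all visits after the second intra-articular corticosteroid injection within a 24 week period should be set to treatment failure". Continuous endpoints are set to missing at the same visits.
- **Other steroid rules.** For parenteral use, "all visits after a subject received any new parenteral corticosteroids (e.g. intravenous and intra-muscular) should be set to treatment failure". IA use has its own bullet. The 10 mg/day average in SAP 4.5.4 sums oral doses only.
- **Joint scoring.** SAP 3.2.3 says "Artificial, ankylosed and missing joints are excluded from swelling and tenderness assessment". It reweights counts when joints are missing and rules out imputing single joints. Protocol 7.3.1.1 leaves out replaced or fused joints. Neither section mentions injected joints.
- **Eligibility.** Exclusion criterion 18 in Protocol 5.2 bars "Any IM, IV or IA corticosteroids within 8 weeks of Day 1", without giving a reason for the interval.

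**The concern.** Put together, these rules leave a first injection shortly before Week 24 with no effect on the analysis. If it quiets the joint, that joint enters TJC28 and SJC28 as zero, and the subject can be counted as a remitter on the primary endpoint because of a local steroid and not the randomised treatment. The square-root joint terms make the score most sensitive when few joints are active, which is the region around 2.6. No planned sensitivity analysis covers IA use.

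At stake is the classification of individual subjects in arms of about 35, where the plan assumes 3% remission on placebo.

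**Working it through.** **1. The plan's own power figure.** SAP 4.13.1 states about 90% power for Fisher's exact test with 35 per arm, 33% against 3%, two-sided 0.05. Exact enumeration of two Binomial(35, p) arms gives 90.9%. All nine cells of SAP Table 11 are reproduced to within one point. The stated least detectable difference of 17% is 0/35 against 6/35 = 17.1%.

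**2. Fall in score when one joint clears.** The formula in SAP 3.2.1 is

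DAS28(CRP) = 0.56√TJC28 + 0.28√SJC28 + 0.36 ln(CRP+1) + 0.014 PtGA + 0.96.

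Take n joints that are both tender and swollen, and hold CRP and PtGA fixed. Clearing one lowers the score by (0.56 + 0.28)(√n − √(n−1)) = 0.84(√n − √(n−1)). To end below 2.6, the starting score must be at least 2.60 and below 2.60 plus the fall. The CRP and PtGA terms together must also be below 2.6 − 0.96 − 0.84√(n−1).

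| Active joints n | Fall | Starting score must be below | Room for CRP + PtGA terms |
|---|---|---|---|
| 1 | 0.840 | 3.44 | 1.64 |
| 2 | 0.348 | 2.95 | 0.80 |
| 3 | 0.267 | 2.87 | 0.452 |
| 4 | 0.225 | 2.83 | 0.185 |
| 5 | 0.198 | cannot cross | negative |

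At n = 5 the score after clearing is at least 0.84 × √4 + 0.96 = 2.64, even with CRP and PtGA at zero. The limit of about four joints is derived for equal tender and swollen counts and shifts when they differ. For example, at 2 tender and 1 swollen the fall is 0.56(√2 − 1) + 0.28 = 0.512.

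**3. Worked cases** (illustrative values, one tender and swollen joint cleared).

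| TJC28/SJC28 | CRP (mg/L) | PtGA | Before | After | Remission after? |
|---|---|---|---|---|---|
| 1/1 | 5 | 30 | 2.865 | 2.025 | yes |
| 2/1 | 5 | 20 | 2.957 | 2.445 | yes |
| 2/2 | 3 | 20 | 2.927 | 2.579 | yes |
| 2/2 | 5 | 20 | 3.073 | 2.725 | no |
| 6/6 | 5 | 30 | 4.083 | 3.903 | no |

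**4. Would setting the joint to missing cure it?** SAP 3.2.3 would then multiply the remaining count by 28/27. In the 1/1 case the remaining count is 0, so the score is still 2.025. In the 2/2, CRP 3, PtGA 20 case it is 2.594. Both subjects remain remitters. Scoring the joint as active leaves them at 2.865 and 2.927.

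**5. Scale.** The documents give no rate of IA use, so the counts here are assumed. One subject is 1/35 = 2.9 points. With the planning test, one, two or three extra placebo remitters per 35 lower power against 33% from 90.9% to 78.6%, 63.5% or 48.3%. The same numbers of extra remitters in an active arm with a true rate of 25% raise power from 68.5% to 78.7%, 86.4% or 91.8%. The two calculations point in opposite directions.

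**The case against.** **The rule is deliberate.** The SAP names IA steroid and grades exposure: any new IV or IM dose is failure, oral use averaging above 10 mg/day is failure, and one IA injection is tolerated, broadly in line with the protocol allowance. This stands as a reason to keep the second-injection rule. It does not settle how the injected joint is scored.

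**The affected range is narrow.** IA use is meant for severe flares, and a subject flaring in many joints cannot cross on one joint. Hips, ankles and toes are outside the 28. The effect must also last until the visit. All of this stands. However, neither document defines a severe flare by joint count, and the one-joint cap fits a flare in a single joint.

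**A reader might infer that placebo remission is inflated and the contrast pulled toward zero.** The documents do not support that. They report no IA use by arm, and Week 12 EULAR non-responders on placebo or any dose below the top one are escalated at Week 14 and counted as failures from then on.

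**A reader might infer that the plan treats IA steroid as distorting joint assessment for eight weeks.** Criterion 18 is an eligibility window covering IM, IV and IA steroid together, with no stated rationale.

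**A reader might take the power figures as the effect on the primary test.** They use the planning test. SAP 4.9.2.2 analyses Week 24 remission with a GEE logistic model.

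**A rule may exist elsewhere.** Protocol 7.3.1 leaves joint-assessment procedure to the Study Reference Manual, which is not available here. IA could also be read as parenteral, since that bullet gives IV and IM only as examples, but the separate IA bullet would then be redundant.

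**Conclusion.** The point holds in a limited form. On the protocol and SAP text, a first IA injection before an efficacy visit has no analysis consequence and the joint is scored as observed. With few active joints and a starting score of 2.60 to about 3.44, clearing one tender and swollen joint can by itself produce remission. This assumes that the joint is among the 28, that the effect is present at the visit, and that the Study Reference Manual holds no contrary rule. A fall in CRP or PtGA after the injection would widen the range.

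The number of subjects is unknown and probably small, and the direction of bias is undetermined. The effect on EULAR response is smaller: 0.27 at 3/3 and 0.14 at 10/10, against an improvement threshold of 0.6. This is a cheap improvement to the primary endpoint definition. It does not show that the planned result would be wrong.

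**What to change.** Keep the second-injection failure rule and the protocol allowance as they are. Before unblinding:

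1. Amend SAP 3.2.3, including the sentence that rules out imputing single joints, so that a joint given IA steroid is scored as tender and swollen at efficacy visits within a prespecified window. Apply this to TJC28/68, SJC28/66 and every index built on them. Eight weeks is an assumption borrowed from criterion 18 and should be labelled as such. Do not set the joint to missing (step 4). Do not carry forward its last recorded state either: a flare that starts between visits may follow a quiet assessment.
2. Record the injected joint on the concomitant medication entry, and list the affected subjects.
3. If the joint is not recorded, prespecify an analysis of Week 24 remission that treats any IA injection in the window as non-response.
4. If the Study Reference Manual already has an injected-joint rule, cite it in the SAP. State that IA use falls outside the parenteral bullet, if that is the intent.
5. Reconcile Protocol 6.11.3.1, which counts joints, with SAP 4.5.2.1, which counts injections. Repeat injection of one joint is treated differently under the two.

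The cost is SAP wording, one derivation and possibly one data field. The downside is slightly conservative scores in the few injected subjects. The change does not alter Week 12 escape decisions already made, and it does not correct any effect of the injection on PtGA or CRP.
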